Our longitudinal mixed-methods study will use a one-group repeated measures intervention design coupled with qualitative methods to provide a comprehensive view of the feasibility, acceptability, and preliminary effects of the MOMS intervention.^{167,168} Semi-structured interviews, recruitment and retention numbers, and participant logs will be used to evaluate feasibility and acceptability of the intervention (Specific Aim 1). Recently collected archival comparison group data from an existing study described in Section D.2. below will be used to contribute to explorations of preliminary effects of the intervention by comparing longitudinal psychobehavioral data, birth weight data, and genome-wide and gene-specific DNAm data (Specific Aims 2 and 3).

Screening: Interested individuals will contact the study staff via email or phone call. Study staff will call the participant back to conduct screening. Screening will be done by phone in order to minimize burden of individuals, particularly those who may not be eligible. The screening script is uploaded in this application and is focused on the eligibility criteria. (see attached screening scripts document) No screening questionnaire data will be retained.

Following an initial phone interview in which the study will be generally discussed, eligible and interested women will be invited to an in-person meeting at a private and mutually agreed upon location (e.g., private room in School of Nursing or obstetrician♦s office) or a phone meeting (for women who have transportation issues/parenting conflicts) to engage in the consent process with the PI/PD. In this formal consenting process, the potential participants♦ questions will be fully answered. If a woman discusses the consent by phone, she will be emailed or mailed the consent form so that she has time to read it prior to the phone discussion; the research staff member will discuss it extensively with her and, when she is ready, obtain verbal consent. The woman will then sign a hard copy of the Consent Form and receive a copy of the signed form when she meets with the research staff member for the first blood draw/ yoga session.

Intervention: The MOMS intervention incorporates key components informed by the SM^{98,110} and physical activity (PA) literature,^{108,114} as well as our research about the acceptability of yoga as a mode of mindful PA.¹³⁷

Summary of Study Visits:

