(a) **Depressive symptom severity:** Depressive symptom severity will be evaluated using the Patient Health Questionnaire (PHQ-9), a widely used instrument which has been validated during pregnancy.¹⁶⁹ The PHQ-9 includes self-report items regarding depressive symptoms over the past two weeks. Total scores range from 0-27: 0-4 indicates minimal depression, 5-9 mild depressive symptoms, 10-14 moderate depressive symptoms, 15-19 moderately severe depressive symptoms, and =20 severe depressive symptoms. For analysis purposes, presence of depressive symptoms will be defined as a score =10 on the PHQ9. The PHQ-9 includes a question on suicidal ideation,^{202,203} which will be used for monitoring for adverse events as described in the Protection of Human Subjects section. Because the archival comparison group database includes the Edinburgh Postnatal Depression Scale (EPDS)¹⁸⁰ in the pregnancy and postpartum assessment, we will also administer this survey at the same timepoints. The EPDS is a widely used and validated measure of depressive symptoms, with 10 questions appropriate for the prenatal and postpartum woman; a score =10 (range 0-30) suggests possible depressive symptoms. Guidelines regarding management of participants with depressive symptoms or suicidal thoughts are detailed in the Protection of Human Subjects section but in brief, the researchers will be poised to assess further and make referrals to appropriate community organizations, healthcare providers, or emergency departments in cases of psychological distress (score =20 on PHQ9 and/or suicidal ideation) or physical injury. (b) **Stress:** The Perceived Stress Scale-10 (PSS-10), a widely used, psychometrically sound instrument, will assess the degree to which a participant perceives stress in her life during the past month.¹⁸¹⁻¹⁸⁵ The PSS-10 asks respondents to report about feelings such as unpredictability, uncontrollability, and overloading of stress in their lives; scores range from 0-40; higher scores correspond to a higher perceived stress level.¹⁸⁴ (c) **Anxiety:** Current levels of anxiety (state anxiety) will be evaluated with the State-Trait Anxiety Inventory, Form Y (STA). This study focuses specifically on state anxiety, as this score is sensitive to women's anxiety during pregnancy and is more likely to demonstrate change within an intervention period.^{190,204} This measure yields reliable and valid scores.¹⁸⁷⁻¹⁸⁹ The STA scores range from 20-40, with higher scores representing higher levels of state anxiety. (d) **Rumination:** Rumination, or repetitive self-critical thinking, will be evaluated with the 10-item Ruminative Responses Scale (RRS) which assesses the propensity to ruminate in association with sadness or depression. A psychometrically sound and widely used instrument, the RRS asks respondents to rate how often they experience various aspects of rumination.¹⁹³ The RRS has two factors of brooding (self-critical pondering) and reflecting (emotionally-neutral pondering or brainstorming). (e) **Self-Efficacy for Physical Activity:** The Physical Activity Self-Efficacy Scale (PASES)^{194,195} is an eight question scale which contains items about SM of physical activities and social support regarding PA. This psychometrically sound scale was selected because of its specific focus on SM of PA. Originally designed for adolescents, the wording has been slightly adapted for an adult sample. (f) **Maternal-Fetal/Child Attachment:** The Maternal-Fetal Attachment Scale (MFAS)^{32,198} assesses the extent to which women have an affiliation and interaction with their unborn child (during pregnancy) and their infant (during PP). Maternal depression has a proximal effect on maternal-child attachment,¹⁷ hence it is highly relevant to evaluate attachment in relation to an intervention designed to address depression.

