Following IRB approval, 41 pregnant women at 12-20 weeks gestation will be recruited from the Virginia Commonwealth University Health System (VCUHS) and community obstetric clinics, to participate in the MOMP intervention. Potential participants must be less than 28 weeks pregnant at the time of starting the 12-week prenatal yoga classes. Additional inclusion criteria are as follows: (1) age 18; (2) self-report of depressive symptoms prior to pregnancy; (3) current depressive symptoms at a moderate-to-severe level, as defined by a score ≥ 10 on the Patient Health Questionnaire (PHQ9);¹⁶⁹ (4) able to read, write, and understand English; (5) self-identify as Black/African American (AA) or White (matching demographics of archival data used for comparison groups); (6) absence of suicidal ideations, psychosis, or mania (measured with MINI Neuropsychiatric Interview as a screening tool);¹⁷⁰ (7) absence of pregnancy complications/physical conditions making PA inadvisable;¹²² (8) has not engaged in a consistent mindfulness-based PA routine during the pregnancy (such as yoga or similar activities more than once per month). Data about use of UC for depression (medications, psychotherapy) will be collected at multiple timepoints and included as covariates in analyses.

For the comparison group: Archival data from an existing IRB-approved study (NIMHD2P60MD002256, PI: [name]) includes pregnant women recruited from the VCUHS and area clinics who did not receive the MOMP intervention yet were followed throughout their pregnancies and into the postpartum period, using psychobehavioral, birth weight, and DNA methylation measures

identical to those proposed in this study. The de-identified data will be used to form two age/race-matched comparison groups: (a) positive comparison group (n=40): pregnant women with clinically relevant depressive symptoms receiving the UC; and, (b) negative comparison group (n=40): pregnant women without clinical depressive symptoms.

5. * List the study exclusion criteria:

If individual does not meet the inclusion criteria listed above, they are ineligible for the study.

6. * Check all participant groups that will be included in this study or discernable in the research data/specimens. In particular, if you will know that a regulated vulnerable population (children, pregnant women, or prisoners) is involved in the study, be sure to check them:

Healthy volunteers

Children

Emancipated minors

Pregnant women

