- 5. * Is it likely investigators could discover a participant's previously unknown condition (eg disease, suicidal thoughts, wrong paternity) or if a participant is engaging in illegal activities:**

Yes
 No

- 6. If yes, explain how and when such a discovery will be handled:**

During screening: if an individual contacts study staff and is ineligible for the study but has a concerning psychological risk (e.g. high score on the PHQ9 (or endorses suicidality) or signs of psychosis or mania), she will be provided with phone numbers to the crisis/emergency response teams of local mental health agencies (Henrico County Community Services Board: [contact]; Chesterfield County Community Services Board: [contact]; Richmond Behavioral Health Authority: [contact]) and/or will be directed for emergent care at the local emergency department.

For participants: It is possible that some participants will experience increased intrapersonal or interpersonal psychological distress as a result of participating in assessment or intervention. In the vast majority of cases, we believe that any increased distress experienced will be mild and transitory in nature.

IF Significant worsening of depressive symptoms= participant scores ≥ 20 on the PHQ9 (with no endorsement of suicidality) --> PI will contact participant and conduct the MINI suicide module as soon as information is obtained. If suicide risk is low ($=8$), applicant will ask participant to be in touch with her healthcare provider. Contact information for local resources will be provided, as needed (e.g. Henrico County Community Services Board: [contact]; Chesterfield County Community Services Board: [contact]; Richmond Behavioral Health Authority: [contact]; local emergency departments).

IF endorsement of suicidality item on PHQ9 or verbal report of suicidality --> PI will contact participant and conduct the MINI suicide module as soon as information is obtained. If suicide risk is high ($=9$), PI will ensure participant is accompanied by a family member or friend to their healthcare provider or local emergency department for immediate evaluation. PI will contact study team and clinical psychologist Co-I ([name]) and/or psychiatrist-collaborator ([name]) to assess the concern (within 1 day).

See also page 8 on the DSMP.

- 7. * Describe any potential risks or harms to a community or a specific population based on study findings:**
n/a

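### Item 6 ties the screening-stage referral step to ineligibility, so an eligible woman with a PHQ-9 of 20 to 24 has no stated step at the screening call

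*Combined protocol and SAP*

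**What the plan says.** Item 6 explains, in two parts, how staff will handle a previously unknown condition.

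The screening part applies where this condition is met: "During screening: if an individual contacts study staff and is ineligible for the study but has a concerning psychological risk". Its examples are a high PHQ-9 score, suicidality, and signs of psychosis or mania. The response is crisis-team phone numbers for three local agencies and/or direction to an emergency department. It gives no number for a high score.

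The second part covers participants. A PHQ-9 of 20 or more without suicidality leads to contact by the PI and the MINI suicide module. If risk is low, she is asked to contact her own provider, and local resources are given as needed.

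On eligibility, Study Population, item 4, asks for "current depressive symptoms at a moderate-to-severe level, as defined by a score" of at least 10, with no ceiling. Criterion 6 requires "absence of suicidal ideations, psychosis, or mania (measured with MINI Neuropsychiatric Interview as a screening tool". Item 5 gives no separate exclusion list; a woman is excluded only by failing an inclusion criterion.

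On the scale and the screening record, Research Description, item 4, states "Total scores range from 0-27", "The PHQ-9 includes a question on suicidal ideation" and "No screening questionnaire data will be retained". Privacy, item 1, repeats that screening answers are not kept.

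**The concern.** The step is written for women with a concerning finding, but it depends on whether they can join the study. For a high score the two do not go together. The trial seeks women with raised scores, so the high-score example matters most for women whom the ineligibility condition leaves out.

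The harm would fall on an eligible woman who is not enrolled. She would leave the call without the resource numbers and without advice to see her provider. Because her answers are discarded, the call is the only stated point at which that score could be acted on if she goes no further.

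**Working it through.** No figure in the plan needs reproducing. The check is a comparison of text plus one short sum.

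**Who is covered at the screening call**

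| Woman at screening | Eligible? | Step in item 6 at that call |
|---|---|---|
| Suicidality, psychosis or mania | No (criterion 6) | Crisis numbers and/or emergency direction |
| PHQ-9 of 22, none of those, regular yoga practice | No (criterion 8) | Crisis numbers and/or emergency direction |
| PHQ-9 of 22, none of those, all other criteria met | Yes | None stated |

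The last two rows differ only in yoga practice.

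**The score band**

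1. Lower end: 20, the cut-off in item 6's part for participants. Research Description, item 4, uses the same value: "in cases of psychological distress (score =20 on PHQ9 and/or suicidal ideation) or physical injury". The equals sign there appears to be a lost at-or-above sign.
2. Points per item: 27 / 9 = 3. This assumes nine equally scored items; the documents give only the total.
3. Highest total with the suicidality item at 0: 27 − 3 = 24.
4. Band: 20 to 24. A total of 25 needs at least 25 − 24 = 1 point on the suicidality item, which brings criterion 6 into play, so 25 to 27 is left out.

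**What happens afterwards**

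- If she enrols, a baseline PHQ-9 of 20 or more triggers the part for participants. Recruitment is at 12–20 weeks' gestation (Study Population, item 4) and baseline sampling at 12–22 weeks (Research Description, item 4). If screening takes place at the recruitment age, the baseline window closes at most 22 − 12 = 10 weeks later for a woman screened at 12 weeks, and 22 − 20 = 2 weeks later for one screened at 20 weeks. Classes must also start before 28 weeks.
- If she declines or does not attend, she never becomes a participant, and the documents give no route by which the discarded screening score prompts anything later.

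**Whether other text fills the gap**

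- Research Description, item 4: the readiness to assess and refer appears in a sentence about managing participants.
- 2.1 Recruitment and Informed Consent: referrals are available on request, so she must attend and ask.
- 2.2 Protections against Risk: community referrals as needed, under distress from assessment and treatment procedures.
- The training paragraph at the start of the supplied text: staff are oriented to processes for elevated depression scores, but the process is not described.

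None of these states a step for an eligible woman at the screening call.

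**The case against.** The strongest reply is that the condition has a rationale. An ineligible woman has no further study contact, so the call is the only chance to help her. An eligible, interested woman goes on to a consent discussion with the PI, a nurse practitioner, or the project director, an RN. She has also met the MINI criterion on suicidality, psychosis and mania. Staff are trained on elevated scores. Item 6 is a form field that refers on to page 8 of the DSMP, and the words used on a call belong in the screening script. Those two documents, the adverse-event protocol and the manual of operations were not supplied and may already cover her.

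Most of this stands, and it is why the point is small. It does not help the woman who declines or does not attend, and it does not make the sentence in item 6 right.

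Stronger readings are tempting, but the documents do not support them:

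- A reader might infer that women with suicidal thoughts are missed. Suicidal ideation makes a woman ineligible, so the screening step already reaches her.
- A reader might infer that the wait until baseline is open-ended, because the consent tables let an eligible woman take as long as she needs to decide. That wording guards against pressure, and the gestational-age limits bound the interval.
- A reader might infer that the study has no process for high scores. The training paragraph and the unsupplied attachments rule out that conclusion.

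**Conclusion.** The point holds as a minor patient-safety correction to the wording of item 6. The stated response at screening depends on eligibility where it should depend on the finding. The women left out are those who are eligible, score 20 to 24, and show no suicidality, psychosis or mania. For those who enrol, the gap closes at baseline if they still score 20 or more. For those who decline or do not attend, item 6 never applies.

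What is missing is limited to resource numbers and advice to contact a provider. The documents give no distribution of screening scores and no consent rate, so the number affected is unknown. The conclusion rests on the supplied text only, on the assumed item scoring for the upper end of 24, and on taking the protocol's cut-off of 20 as the meaning of high for eligible women. There is no effect on design, sample size or analysis.

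**What to change.** In item 6, strike the six words that set the ineligibility condition, so that the step applies to any screened woman with a concerning finding, whether or not she is eligible or enrols.

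- Leave the present crisis numbers and/or emergency direction in place for everyone who now receives them, including ineligible women whose only finding is a high score. Do not narrow the term high for them: the protocol labels "15-19 moderately severe depressive symptoms", which staff may already treat as high.
- For eligible women, define the high-score trigger as a PHQ-9 of 20 or more, the cut-off already used for participants. They all score at least 10, so an undefined trigger would be hard to apply.
- Add advice to contact her healthcare provider.
- Check that the screening script and page 8 of the DSMP agree. If they already cover eligible women, item 6 only needs to match them.

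The cost is one sentence, a matching line in the script if needed, and about a minute on each affected call. No extra staff, procedure or data are required.

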Weekly contact by study staff (phone or email per participants' choice): Study staff will maintain regular contacts in the mode of participants' choice during the 12 weeks of the intervention. This is intended to help with retention as well as monitoring for adverse events. Study staff will collect data about minutes of physical activity during these weekly phone contacts. No survey or other data will be collected during this contacts, unless a participant verbalizes a physical or psychological adverse event.

Study Visit #7 (Intervention Week 6): Participants will be asked to complete questionnaires at the midpoint of the 12-week intervention at home electronically (if they have computer access at home) or in paper/pencil form (for those without sufficient comfort levels or access to a computer~~to~~RA will pick them up at participants~~to~~ next class).

Study Visit #14-- Last visit during pregnancy: Participants will complete another set of questionnaires electronically or in paper/pencil format. A blood sample will also be collected (8 ml blood by venipuncture in 2 EDTA [purple top] tubes).

Study Visit #15-- Postpartum Visit/Interview Session: Each participant will meet with study staff (RA, PD, and/or PI) to complete the questionnaires and participate in a semi-structured interview. Specific questions for this semi-structured interview are found in the Study Interview Guides/Scripts document. This interview will be audiotaped (and later transcribed).

Note: if a participant chooses to withdraw from the study, they will be given the opportunity to give their reasonings for withdrawal in the form of a short interview with research staff.

**** For Addendum Feb 2018: "Long-Term Follow-Up" study visit:** participants who "opted-in" to being contacted for future study will be contacted via email and/or phone about answering survey questions. Participants will give consent via REDCap (or in rare instances, may choose paper & pencil, which will be completed in-person with the research nurse) and will answer survey questions, using the same measures that have been used at previous study visits.

STUDY MEASURES

** SEE TABLE 1. STUDY MEASURES BY TIMEPOINTS

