Aim 2: Examine the potential effects of the MOMS intervention on measures of maternal psychological symptoms assessed at multiple time points (Table 1) and on the baby²⁰⁶s birth weight, with the primary variable of interest, depressive symptoms, measured by the PHQ-9. Means, variances and covariances/ correlations along with 95% confidence intervals for each of the three groups (intervention [MOMS], comparison group with depressive symptoms [positive], and comparison group without depressive symptoms [negative]) will be calculated for each of the four study time points (baseline [BL], IW6, IW12, postpartum [PP]). A mixed linear model (MLM) will be fit to the data. The model will include one between-subjects effect (Group: MOMS, positive comparison, negative comparison), one within-subject effect (Time: BL, IW6, IW12, PP), and the interaction between group and time. This model will allow estimation of changes from baseline in levels of psychological symptoms within and between groups at each time point. Possible covariates, such as the initiation of UC (medications, psychotherapy), will be fully explored during analysis. Data from participants who drop out of the intervention will be retained in the analytical portion of the study according to intent-to-treat principles. Correlations will be calculated between baby²⁰⁶s birth weight and group (intervention, positive comparison, negative comparison). Figure 2 summarizes data collection timepoints for the study in relation to the archival comparison group database.

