- 8. * Describe criteria for withdrawing an individual participant from the study; such as safety or toxicity concerns, emotional distress, inability to comply with the protocol, etc.:**

We do not anticipate withdrawing a participant from the study, unless she (a) is no longer pregnant due to spontaneous or therapeutic abortion prior to the end of the 12 week intervention period, or (b) she is unable to comply with the protocol and attend a majority of the study sessions, or (c) participant reports any of the following and are advised to cease gentle yoga-based physical activities by their healthcare provider: new vaginal bleeding, new dizziness, new/increased shortness of breath, chest pain, new acute headache, new calf pain/swelling, preterm labor/ delivery (regular, frequent, painful contractions), decreased fetal movement, new fluid leaking from the vagina.

- 9. * Summarize any pre-specified criteria for stopping or changing the study protocol due to safety concerns:**
Participants will be asked to stop engaging in the prenatal yoga classes if they experience any of the symptoms identified by ACOG as reasons to cease physical activity (list in item #8 above). See DSMP.

- 10. Where appropriate, discuss provisions for ensuring necessary medical, professional, or psychological intervention in the event of adverse events to the subjects:**
see data safety monitoring plan

11. * Describe any potential for direct benefits to participants in this study:

We cannot guarantee any direct benefits to participants in the study. The research may yield new knowledge about biobehavioral self-management approaches as adjunctive therapies for perinatal depressive symptoms.

12. * Describe the scientific benefit or importance of the knowledge to be gained:

This study will provide information about the feasibility, acceptability, and preliminary effects of a biobehavioral self-management approach for perinatal depressive symptoms. This line of research will contribute to the body of knowledge about adjunctive therapies for depressive symptoms in pregnancy, a serious problem which contributes to poor maternal-child outcomes. Ultimately, this will contribute to the development and implementation of theoretically driven depression prevention/ resiliency building interventions and measurement of appropriate biobehavioral outcomes to determine the effectiveness of interventions.

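### Item 8 lets a woman be withdrawn from the study for poor attendance or a symptom, and no available text says her assessments continue

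*Combined protocol and SAP*

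**What the plan says.** Item 8 of the section on risks, discomforts, potential harms and benefits answers the form's question about withdrawing an individual participant. It opens "We do not anticipate withdrawing a participant from the study, unless she" and then gives three grounds.

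- Ground (a) is loss or termination of the pregnancy before the 12 weeks are over. It is outside this point.
- Ground (b) is that "she is unable to comply with the protocol and attend a majority of the study sessions".
- Ground (c) covers women who report a listed symptom and "are advised to cease gentle yoga-based physical activities by their healthcare provider". The list includes "preterm labor/ delivery (regular, frequent, painful contractions), decreased fetal movement, new fluid leaking from the vagina".

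Item 9, on stopping for safety, is narrower in its consequence: "Participants will be asked to stop engaging in the prenatal yoga classes if they experience any of the symptoms identified by ACOG".

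Three other places bear on what happens to the data:

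- Data Analysis Plan, Aim 2: "Data from participants who drop out of the intervention will be retained in the analytical portion of the study according to intent-to-treat principles".
- Study Visit #15 (postpartum): "Each participant will meet with study staff (RA, PD, and/or PI) to complete the questionnaires and participate in a semi-structured interview". No attendance condition is attached.
- The note after Study Visit #15: "if a participant chooses to withdraw from the study, they will be given the opportunity to give their reasonings for withdrawal". The feasibility and acceptability measures likewise describe an open-ended interview for a woman who drops out.

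**The concern.** Grounds (b) and (c) are both about taking part in the yoga intervention, but the stated consequence is leaving the study. The Aim 2 plan speaks of women who leave the intervention and says their data are kept. Keeping data in hand is different from continuing to collect data, and no available text makes that link for women withdrawn under item 8.

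If staff apply item 8 literally, outcomes go missing for reasons that may be related to those outcomes: poor adherence under (b), a pregnancy complication under (c). Three aims are touched.

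- **Aim 1 (the primary aim):** a woman withdrawn under (b) counts as not retained because she did not attend, even if she would have answered every questionnaire. Adherence and retention are meant to be separate findings.
- **Aim 2:** follow-up scores and birth weight can be lost. Ground (c) lists preterm labor or delivery, and birth weight is an Aim 2 outcome.
- **Aim 3:** the pre/post comparison needs a second blood sample from the same woman.

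**Working it through.** The plan gives no figure for this rule, so the check is mainly a comparison of texts, with a little arithmetic for scale.

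**1. Does any text continue assessments after an item 8 withdrawal?**

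- The Aim 2 intent-to-treat sentence concerns women who leave the intervention, and it says their data are retained. It does not say that later data are sought, and it does not mention removal from the study.
- Study Visit #15 covers each participant. One fair reading is that a woman who has stopped classes is still a participant and is seen. Another is that a woman withdrawn from the study no longer is one.
- The contacts described specifically for women who leave are interviews about reasons and experience.
- The long-term survey is offered to women who opted in to future contact. The text is silent on withdrawn women, and the survey would not replace the week-6, week-12 or 6-week postpartum assessments.

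None of these settles the question.

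**2. Which outcomes can earlier data rescue?**

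- Questionnaire scores, partly. The mixed linear model (baseline, week 6, week 12, postpartum) can use the visits a woman completed. Its estimates then rest on a missing-at-random assumption, which withdrawal for adherence or symptoms does not assure.
- Birth weight, not at all. Under Objective Measures, mothers report it at the postpartum visit only.
- Paired methylation, not at all. Aim 3(b) uses paired t-tests, and blood is drawn only at visits 1 and 14. A woman without the second sample contributes no pair.

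**3. When can the loss occur?** Ground (c) can arise in any week, so the week-6 questionnaires can be lost too. Under (b), if the count is of the 12 classes, a majority goes out of reach only after the sixth missed class (12 − 6 = 6, below the 7 needed). The main exposure under (b) is therefore week 12 and postpartum.

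**4. What is a majority?** The term *study sessions* is not defined. The Summary of Study Visits counts 15 contacts: visit 1, 12 classes (visits 2 to 13), visit 14 and visit 15.

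- Majority of 12 classes: 7.
- Majority of 15 contacts: 8.

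**5. Scale.** The Research Description and inclusion criteria give 41 intervention women. One withdrawn woman who would otherwise have responded costs 1/41 = 2.4 percentage points of completion at each later time point. For context, the sample-size justification cites 20–40% attrition in the team's previous studies: 41 × 0.80 = 32.8 and 41 × 0.60 = 24.6, or about 25 to 33 women. That is attrition overall. The share due to item 8 cannot be derived from the documents.

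**The case against.** The strongest reply is that this rests on silence. Item 8 never mentions assessments. Its words about withdrawal from the study echo the form's own prompt, and the answer begins by saying withdrawal is not expected. The text that does address data, namely the intent-to-treat sentence and the unconditional postpartum visit, leans towards continued follow-up. The safety monitoring plan, the adverse-event protocol and Table 1 were not available, and a follow-up rule could well sit there. The Data Analysis Plan for Aim 1 already records completion at each time point, sessions attended and attrition, and describes reasons for attrition. This is also a pilot that disclaims power for effectiveness.

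Much of this stands. It is why the point is a request to state the rule, with no estimate of harm. It does not remove the point: item 8 does state grounds for leaving the study, and the intent-to-treat sentence does not reach them.

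A reader might infer that items 8(c) and 9 contradict each other. They do not. Item 9 is triggered by a symptom alone and stops classes. Item 8(c) needs the symptom and the provider's advice to stop. The text on Study Visits #2–#13 and the protections against physical harm show the sequence, with provider consultation coming between the two.

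Nor does the ambiguity in (b) by itself show lost outcomes. A woman with 5 or 6 classes plus visits 1, 14 and 15 has 8 or 9 of 15 contacts and meets one majority but not the other. Having attended visits 14 and 15, she has already reached the late assessments. Ground (b) also reads as a judgement that she is unable to comply, not as an automatic cut-off. The undefined term needs only a short clarification.

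**Conclusion.** The point holds as a gap with a plausible cost. Item 8 permits withdrawal from the study on grounds tied to adherence or symptoms, and no available text says that the scheduled assessments continue afterwards. Applied literally, this works against the intent-to-treat principle in the Aim 2 plan. For birth weight and the Aim 3 paired comparison, earlier data cannot make up the loss.

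The size is unknown. Withdrawals are not anticipated, the number affected may be small, and no estimate of bias is offered beyond 2.4 percentage points of completion per woman. The conclusion assumes that the documents not available do not already settle the matter.

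Two stronger conclusions are tempting and are not supported. One is that the plan orders assessments to stop after an item 8 withdrawal; it does not say so. The other is that missing data will differ between the MOMS group and the archival groups. A rule tied to classes can apply only to MOMS women, so a difference is possible. However, the archival study's withdrawal rules and completeness are not given, and the statement that those women were followed into the postpartum period describes design, not completion.

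Priority: low to moderate.

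**What to change.** Reconcile item 8 with the intent-to-treat sentence in the Aim 2 plan:

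1. State that grounds (b) and (c) end class participation and not study follow-up. Women who leave on these grounds without withdrawing consent are still asked for the already scheduled questionnaires, the birth-weight report and, where they agree, the second blood sample.
2. State whether *study sessions* in (b) means the 12 classes or the 15 contacts.
3. In the Aim 1 summaries, show (b) and (c) cases separately from voluntary dropout, with all consented women as the denominator.

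If the safety monitoring plan or another document already says this, a cross-reference in item 8 is enough. No rule on who may do yoga changes, and ground (a) is left as it is.

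The cost is protocol wording, a few more contacts using questionnaires already administered electronically, and some second blood draws where agreed. Completion, adherence or effect figures may look less favourable.
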